- h. The patient has complied with home spirometry and diary entry on at least 5 of the last 7 days prior to the visit including:
 - completion of daytime and night-time asthma symptom scores
 - completion of daytime and night-time rescue medication use, whether used or not
 - completion of the morning FEV₁ and PEF by handheld device
 - confirmed daily use of asthma maintenance medication as prescribed
- i. The patient has not had an upper respiratory infection (URI) or lower respiratory infection (LRI) during the run-in period. Patients who develop a URI or LRI during the run-in period may be discontinued from the study and allowed to rescreen 2 weeks after resolution of symptoms. They must have a negative test for COVID-19 active infection.
- j. The patient has used rescue medication or had a daytime or night-time asthma symptom score ≥ 1 on 3 or more days in the 7 days prior to the randomization visit as reported in the patient diary.

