6.1.3. Asthma Control Days

An asthma control day is defined as a day on which the patient uses zero puffs of inhaled SABA, has no night-time awakenings, and experiences no asthma exacerbations.

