6.1.5. Asthma Symptom Score

The asthma symptom score will be determined from the information recorded in the asthma control diary. A Likert-style scale will be used to quantify symptomatology. This scale has been

used previously to assess changes in asthma symptoms in response to novel asthma treatments ([Shapiro et al 2000](#)).

Asthma symptom scores should be determined twice daily, in the morning and evening:

Daytime Symptom Score (determined in the evening)

- 0=No symptoms during the day
- 1=Symptoms for 1 short period during the day
- 2=Symptoms for 2 or more short periods during the day
- 3=Symptoms for most of the day which did not affect my normal daily activities
- 4=Symptoms for most of the day which did affect my normal daily activities
- 5=Symptoms so severe that I could not go to work or perform normal daily activities

Night-time Symptom Score (determined in the morning)

- 0=No symptoms during the night
- 1=Symptoms causing me to wake once (or wake early)
- 2=Symptoms causing me to wake twice or more (including waking early)
- 3=Symptoms causing me to be awake for most of the night
- 4=Symptoms so severe that I did not sleep at all

Symptom-free days are defined as 24-hour periods with asthma symptom score of 0.

Asthma control days are defined as 24-hour periods with asthma symptom scores of 0 and no rescue medication use.

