9.5.2. Secondary Efficacy Endpoints

[figure not shown]
The secondary efficacy endpoints are:

- overall weekly well-controlled asthma status defined by the asthma control composite score and weekly asthma control status (Yes versus No) from week 1 through 12 and overall weekly well-controlled asthma status from week 1 through 16
- overall changes from baseline in the weekly average of daily morning trough (pre-rescue bronchodilator) FEV₁ as measured by a handheld device over 12 weeks from week 1 through 12 and over 16 weeks from week 1 through 16
- overall changes from baseline in weekly average of rescue medication use over 12 weeks from week 1 through 12 and over 16 weeks from week 1 through 16
- changes from baseline in percentage of asthma control days (no symptoms and no rescue medication use) over 12 weeks from week 1 through 12 and over 16 weeks from week 1 through 16
- change from baseline in clinic-based standardized baseline-adjusted morning trough FEV₁ at week 16
- proportions of patients who achieve clinic-based FEV₁ $\geq 80\%$ predicted at weeks 12, 16, and at endpoint
- proportions of patients who achieve forced expiratory flow at 25% to 75% of FVC (FEF₂₅₋₇₅) $\geq 70\%$ predicted at weeks 12, 16, and at endpoint
- time to first CAE throughout the study
- changes from baseline in Asthma Control Questionnaire (ACQ-6) at weeks 12 and 16
- changes from baseline in ACT at weeks 12 and 16
- changes from baseline in Standardized Asthma Quality of Life Questionnaire (AQLQ[S]) at weeks 12 and 16

- proportions of patients who achieve FEV₁:FVC ratio ≥ 0.80 at weeks 12, 16, and at endpoint

9.5.3.

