The SAP is intended to be in agreement with the protocol, especially with regard to the primary and all secondary endpoints and their respective analyses. However, the SAP may contain more details regarding these particular points of interest, or other types of analyses (eg, other endpoints). When differences exist in descriptions or explanations provided in the study protocol and this SAP, the SAP prevails; the differences will be explained in the clinical study report.

When the study is terminated early due to futility at interim analysis or due to sponsor's strategic decision, the planned analyses may be simplified to present the necessary information for an abbreviated clinical study report (CSR). The Bayesian analysis for the primary efficacy endpoint and the statistical analyses for some of the secondary efficacy endpoints may not be conducted for the abbreviated CSR. The analysis plan will be followed where applicable.

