6.3.4. Changes From Baseline in Percentage of Asthma Control Days (No Symptoms and No Rescue Medication Use) Over 12 Weeks From Week 1 Through 12 and Over 16 Weeks From Week 1 Through 16

An asthma control day is defined as a day on which the patient uses zero puffs of inhaled SABA, has no night-time awakenings, and experiences no asthma exacerbations.

The post-baseline analysis window for over 12 weeks will be from the first day of IMP up to the day 84. The post-baseline analysis window for over 16 weeks will be from the first day of IMP up to the day 112. Baseline window will include days up to the first dose of IMP.

Percentage of asthma control days in each analysis window will be calculated as

$$(\sum \text{asthma control days in an analysis window} / \text{number of non-missing e-diary days during the analysis window}) * 100$$

The changes from baseline in percentage of asthma control days over 12 weeks (up to day 84) and over 16 weeks (up to day 112) will be analyzed, respectively, using analysis of covariance (ANCOVA) including baseline percentage of asthma control days, randomization stratification factors, and treatment group in the model.

6.3.5. Change From Baseline in Clinic-Based Standardized Baseline-Adjusted Morning Trough FEV₁ at Week 16

The analysis will be based on data collected at site visits. FEV₁ measures at visit 1/screening, visit 3/DoR, visit 4/week 1, visit 5/week 2, visit 6/week 4, visit 7/week 8, visit 8/week12, and visit 9/week 16 or the early withdrawal visit. The analysis will include post-baseline data up to the visit 6/week 16. Baseline will be the last measure before the first dose of IMP.

The change from baseline in clinic-based morning trough FEV₁ at week 16 will be analyzed using MMRM method in a manner analogous to the analysis as described in Section 6.3.2. Baseline clinic-based morning trough FEV₁ will be used in model. WEEK will denote to the visit.

For model-based results, only week 16 results will be displayed. Summary statistics will be provided by visit/week.

6.3.6. Proportions of Patients Who Achieve Clinic-Based FEV₁ \geq 80% Predicted at Weeks 12, 16, and at Endpoint

The percent of predicted FEV₁ will be measured by handheld device. The analysis will be based on data collected at site visits and will be applied in patients with baseline FEV₁ $<$ 80% Predicted.

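### SAP 6.3.4 derives asthma control days without daytime symptoms, which contradicts its own endpoint title and Protocol 6.1.5

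*SAP*

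**What the plan says.** The protocol defines the term twice. Section 6.1.3, the section devoted to it, begins "An asthma control day is defined as a day on which the patient uses zero puffs of inhaled SABA" and adds the absence of night-time awakenings and of exacerbations. Section 6.1.5, on the symptom score, says "Asthma control days are defined as 24-hour periods with asthma symptom scores of 0 and no rescue medication use".

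The secondary endpoint is named in Protocol 9.5.2 as "changes from baseline in percentage of asthma control days (no symptoms and no rescue medication use". The same label stands in the Synopsis, Protocol 2.1, SAP 1.1, SAP 6.2.3 and the heading of SAP 6.3.4.

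Under that heading, SAP 6.3.4 uses the other rule: "a day on which the patient uses zero puffs of inhaled SABA, has no night-time awakenings, and experiences no asthma exacerbations". The SAP Introduction adds "When differences exist in descriptions or explanations provided in the study protocol and this SAP, the SAP prevails". SAP 15, which lists changes from the protocol, records no change to this definition.

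On baseline, SAP 6.3.3 and 6.3.4 end the window at the first dose and give no start day. SAP 4.2 sets e-diary baselines as an average over the 7 days before randomization.

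**The concern.** The variable to be analysed is not the one its title announces. The precedence clause ranks the SAP above the protocol, but it cannot settle a SAP heading against the SAP text beneath it. Two programmers working from the same section could derive different variables. The study report could also present under a no-symptoms label a percentage that ignores daytime symptoms.

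Two consequences follow:

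- An effect confined to daytime symptoms cannot register in this endpoint.
- Patients who entered on daytime symptoms alone can already be at the ceiling at baseline, with no room to improve.

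The same variable is one of the five secondary endpoints chosen for subgroup analysis in SAP 6.2.3.

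**Working it through.** The plan gives no figure to reproduce, so the check compares the two rules and then works out what each permits at baseline.

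**The rules side by side**

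| Condition | Protocol 6.1.3 and SAP 6.3.4 | Protocol 6.1.5 and endpoint label |
|---|---|---|
| No rescue SABA | required | required |
| Night | no awakenings | night-time score 0 |
| Daytime score 0 | not required | required |
| No exacerbation | required | not required |

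On the Protocol 6.1.5 night-time scale, every score of 1 or more involves waking or not sleeping. The night conditions are therefore practically the same, and the real gap is the daytime score.

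**Enumeration of diary days.** Daytime score 0–5, night-time score 0–4, rescue yes/no and exacerbation yes/no give 6 × 5 × 2 × 2 = 120 possible states. A night-time score of 0 is read as no awakening.

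- Control day under the SAP text: 6 states.
- Control day under Protocol 6.1.5: 2 states.
- Control day under both: 1 state.
- SAP text only: 5 states, with daytime score 1, 2, 3, 4 or 5 and everything else clear. The last is "5=Symptoms so severe that I could not go to work or perform normal daily activities".
- Protocol 6.1.5 only: 1 state, with all scores 0 and no rescue use on an exacerbation day.

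These are logical possibilities, not expected frequencies. They show that neither rule is contained in the other.

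**Illustration over the 84-day window.** Take a patient with no SABA use, no waking and no exacerbation. The SAP text gives 100% however many days have daytime symptoms. Protocol 6.1.5 gives (84 − k)/84 for k such days:

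- k = 12: 85.7%
- k = 24: 71.4%
- k = 42: 50.0%
- k = 84: 0%

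**Baseline ceiling.** Criterion j in Protocol 4.3 requires rescue use or a daytime or night-time score of at least 1 "on 3 or more days in the 7 days prior to the randomization visit as reported in the patient diary". At least 3 days therefore fail the symptom-score rule, and the maximum with n recorded days is (n − 3)/n. Criterion h sets the smallest n: "The patient has complied with home spirometry and diary entry on at least 5 of the last 7 days prior to the visit". A patient who met criterion j on daytime symptoms alone, with no SABA use and no waking, scores 100% under the SAP text.

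| Recorded baseline days | Maximum under 6.1.5 | SAP text, daytime-only patient | Gap, at least |
|---|---|---|---|
| 7 | 4/7 = 57.1% | 100% | 42.9 points |
| 6 | 3/6 = 50.0% | 100% | 50.0 points |
| 5 | 2/5 = 40.0% | 100% | 60.0 points |
| 14 (assumed, if the open window covered the whole run-in) | 11/14 = 78.6% | 100% | 21.4 points |

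**Direction.** Randomization criterion g excludes patients with an exacerbation in the run-in, so at baseline the exacerbation condition removes no day. The SAP percentage is then never below the 6.1.5 percentage. After dosing the exacerbation condition can remove days, so the direction of the difference in the change score is not fixed.

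**The case against.** The strongest reply is that Protocol 6.1.3 is the section devoted to asthma control days and the SAP carries its wording forward faithfully. On that view the label is shorthand, and retitling the endpoint would reconcile the documents just as well. Retitling would indeed restore consistency. But the label appears in six places, and Protocol 3.3 describes assessing asthma control by daily symptom scores and rescue use. Both point to 6.1.5 as the intended rule.

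Second, the ANCOVA in SAP 6.3.4 adjusts for the baseline percentage, and the rule is the same in every arm. This stands in part. The randomized comparison of the derived variable is not biased, and a patient starting at 100% can still contribute if placebo patients deteriorate. Adjustment does not give that patient room to improve, and it does not bring daytime symptoms into the variable.

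Third, the 100% baseline is a corner case: such a patient must also have an ACQ-6 of at least 1.5 and a home FEV₁ of 40% to 80% predicted. That is fair. The percentages are limits for one patient, not estimates for the trial.

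Fourth, daytime symptoms are captured elsewhere, in the ACT, the AQLQ(S) symptom domain and the weekly composite. The trial would not be blind to them. In the composite, however, the symptom criterion is one of three of which two suffice, and none of these measures makes this endpoint match its name.

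Fifth, SAP 4.2 largely answers the baseline-window point. Agreed: it is a matter of consistency, and the 14-day row only shows what the open wording would allow.

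**Conclusion.** The concern holds. SAP 6.3.4 is wrong as written, not merely short of detail: followed literally, it counts days with daytime symptoms as symptom-free control days. For a patient who entered on daytime symptoms alone, baseline can be overstated against the endpoint label by at least 42.9 points with a 7-day diary, and by at least 60 points with five recorded days. This rests on reading a night-time score of 0 as no awakening, and on such a patient having no rescue use and no waking in the window.

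The documents do not give the proportion of these patients or the rate of days with daytime symptoms only. Neither the size nor the direction of the effect on the treatment difference can be derived. The reach is one of twelve secondary efficacy endpoints, plus its subgroup analyses. The primary endpoint is untouched. The definition should be corrected before unblinding.

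**What to change.** - In SAP 6.3.4, define a control day as a 24-hour period with daytime score 0, night-time score 0 and zero rescue puffs, and record the correction in SAP 15.
- Bring Protocol 6.1.3 into line with 6.1.5.
- State whether days within an exacerbation, from the start to the stop date in Protocol 6.1.2, are also excluded. The present wording does not say whether the condition covers the whole episode.
- In SAP 6.3.3 and 6.3.4, give the baseline window a start by referring to the 7 days in SAP 4.2.

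If the sponsor does intend the 6.1.3 rule, the endpoint should be retitled everywhere it appears. That would change the stated endpoint, whereas aligning to 6.1.5 keeps it.

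The cost is wording only, since both symptom scores and rescue puffs are already recorded twice daily. The protocol edit may need the amendment route in Protocol Appendix C. Because the SAP takes precedence, the SAP correction alone would settle the analysis.

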6.3.8. Time to First Clinical Asthma Exacerbation (CAE) Throughout the Study

The time (days) to the first CAE is the interval from the randomization to the occurrence of the first CAE.

The observation for each patient is the interval from randomization to the occurrence of the first CAE, or censoring, whichever occurs earlier. It is derived as:

the date of censoring or the date CAE - the date of randomization + 1.

Patients who early terminated from the study without CAE due to lack of efficacy or an asthma-related AE will be also treated as experiencing CAE at the time of early withdraw visit.

Patients who complete the week 16 visit without CAE will be right-censored at the time of Week 16 visit. Patients without CAE and early withdrawn from the study before the week 16 with reasons other than lack of efficacy or asthma-related AEs will be right-censored at the time of early withdrawal visit.

The Kaplan-Meier (KM) method will be used to estimate and compare the distributions of time to the first CAE between treatment groups. Distribution difference will be compared by a log rank test adjusting for the randomization stratification factors.

[REDACTED]

6.3.9. Changes From Baseline in Asthma Control Questionnaire (ACQ-6) at Weeks 12 and 16

The ACQ-6 is a validated asthma assessment tool that has been widely used. The 6 questions are self-assessments (completed by the patient). Each item on the ACQ-6 has a possible score ranging from 0 to 6, and the total score is the mean of all responses. ACQ-6 will be administered at visit 2/run-in, visit 3/DoR, visit 5/week 2, visit 6/week 4, visit 7/week 8, visit 8/week 12, and visit 9/week 16 or early withdrawn visit.

The mean total score of the ACQ-6 is derived as the average of the individual item scores. For incomplete data, the following rules will apply:

1. Mean total score for a visit will not be calculated if Question 1 is left blank, irrespective of the completion of the remaining questions.
2. A missing score on post-baseline questionnaire for Questions 2-6 will be imputed based on the total scores from the previous visit, as long as at least 3 out of the 5 questions have responses for the current visit (ie, at least half of the remaining questions are answered).

The formula is: (total sum of non-missing scores for the current visit / total sum of scores for the previous visit for questions answered for the current visit) * (score for the missing question on the previous visit)

3. Mean total score at baseline will not be calculated if Question 1 or two or more among Questions 2-6 is left blank. A missing score for Questions 2-6 at baseline will be replaced by an average of the available scores.

The changes from baseline in ACQ-6 mean total score at Weeks 12 and 16 will be analyzed using MMRM method in a manner analogous to the analysis as described in Section 6.3.2. Baseline ACQ-6 total score will be used in the model.

The analysis includes data up to visit 9/week 16.

6.3.10. Changes From Baseline in Asthma Control Test (ACT) at Weeks 12 and 16

The Asthma Control Test (ACT) is a patient self-administered tool for identifying those with poorly controlled asthma comprising 5 items, with 4-week recall (on symptoms and daily functioning). It assesses the frequency of shortness of breath and general asthma symptoms, the use of rescue medications, the effect of asthma on daily functioning, and the overall self-assessment of asthma control measured on a 5-point scale (for symptoms and activities: 1=all the time to 5= not at all; for asthma control rating: 1=not controlled at all to 5=完全ly controlled). Total scores range from 5 (poor control of asthma) to 25 (complete control of asthma), with higher scores reflecting greater asthma control. An ACT score >19 indicates well-controlled asthma. ACT will be measured at visit 3/DoR, visit 6/week 4, visit 7/week 8, visit 8/week 12, and visit 9/week 16 or early withdrawn visit.

The total score will be calculated based on the available data and will be set to missing if any questions are incomplete.

The changes from baseline in ACT total score at Weeks 12 and 16 will be analyzed using MMRM method in a manner analogous to the analysis as described in Section 6.3.2. Baseline ACT total score will be used in the model.

The analysis includes data up to visit 9/week 16.

6.3.11. Changes From Baseline in Standardized Asthma Quality of Life Questionnaire (AQLQ[S]) at Weeks 12 and 16

The Standardized Asthma Quality of Life Questionnaire AQLQ[S]) will be self-administered by patients. The questionnaire is a tool to measure the impact of asthma on a patient's quality of life (physical, emotional, social, and occupational). The questionnaire contains 32 items with a 2-week recall period and uses a 7-point Likert scale (7=not impairment at all to 1=severely impairment). Scores range from 1 to 7, with higher scores indicating better quality of life. The 32 questions (items) in the AQLQ(S) are divided in to 4 domains and the corresponding questions are:

- Symptoms: 6, 8, 10, 12, 14, 16, 18, 20, 22, 24, 29, 30
- Activity Limitation: 1, 2, 3, 4, 5, 11, 19, 25, 28, 31, 32
- Emotional Function: 7, 13, 15, 21, 27
- Environmental Stimuli: 9, 17, 23, 26

AQLQ(S) will be measured at visit 3/DoR, visit 8/week 12, and visit 9/week 16 or early withdrawn visit.

The overall and domain mean scores of the AQLQ will be derived as the average of the corresponding items. For incomplete data, the overall mean score for a particular visit will not be calculated if 3 or more responses are missing with no more than 1 per domain. For the symptom and activity domain mean scores, calculation will require no more than 1 missing item. The mean domain score for the other 2 domains will be regarded as missing if 1 or more item is missing.

The changes from baseline in AQLQ(S) at week 12 and week 16 will be analyzed, respectively, using ANCOVA in a manner analogous to the analysis as described Section 6.3.4. The analyses will be for the overall mean score and mean score of each domain. The baseline in the model will be baseline overall mean score of AQLQ(S) or baseline mean score of AQLQ(S) for the domain, respectively.

6.3.12. Proportions of Patients Who Achieve FEV₁:FVC (Forced Vital Capacity) Ratio ≥ 0.80 at Weeks 12, 16, And at Endpoint

The proportions of patients who achieve FEV₁: FVC ratio $\geq 80\%$ will be analyzed using the repeated measures logistic regression model in a manner analogous to the analysis as described Section 6.3.1. Baseline FEV₁: FVC ratio will be used in the model. The analysis will be applied those with baseline FEV₁: FVC ratio < 0.80 .

The analysis will include data up to visit 9/week 16.

6.4. [REDACTED]

- A horizontal bar chart illustrating the distribution of 1000 samples across 10 categories. The x-axis represents the sample index (1 to 1000), and the y-axis represents the category index (1 to 10). The bars are black and show the count of samples for each category. The distribution is highly skewed, with most samples falling into a few categories, particularly category 10.

Category	Approximate Sample Range	Approximate Sample Count
1	100-200	100
2	100-200	100
3	100-200	100
4	100-200	100
5	100-200	100
6	100-200	100
7	100-200	100
8	100-200	100
9	100-200	100
10	100-200	100

6.4.2.

Term	Percentage
GMOs	85%
Organic	82%
Natural	78%
Artificial	65%
Organic	80%
Natural	75%
Artificial	60%
Organic	70%
Natural	68%
Artificial	55%
Organic	60%
Natural	58%
Artificial	45%
Organic	50%
Natural	48%
Artificial	35%
Organic	40%
Natural	38%
Artificial	25%
Organic	30%
Natural	28%
Artificial	15%

